## **Study site**

55 rural clusters followed through Bandim Health Project's Rural Health and Demographic Surveillance site in Oio, Biombo and Cacheu regions in Guinea-Bissau and 37 urban clusters followed through Bandim Health Project's Urban Health and Demographic System site in Bissau.

Bandim Health Project, [name], Guinea-Bissau

## Protocol changes

- May 2015     Original protocol (*Approved by the Guinean ethical committee June 2015*)
- May 2016     Protocol adapted to include Tokyo 172 strain from BCG Japan (*Approved by the Guinean ethical committee June 2016*)
- May 2017     Definitions of primary and secondary outcomes were clarified. Analyses section was clarified and supplemented by the analysis plan. Sample size considerations were updated.
- The Danish BCG strain was removed from the protocol, since this strain was only used during the pilot phase of the trial.
- June 2017     Study area was expanded to include BHP's urban study area. The protocol format was changed to comply with the current guidelines of the Ethical Committee in Guinea-Bissau.

## **ABBREVIATIONS AND ACRONYMS**

BCG	Bacillus Calmette-Guérin vaccine
BHP	Bandim Health Project
CKI	Community key informant
DTP	Diphtheria, tetanus and pertussis vaccine
EPI	Expanded Program on Immunization
LBW	Low-birth weight
MUAC	Mid-upper-arm-circumference
MV	Measles vaccine
NBW	Normal-birth weight
NSE	Non-specific effect
OPV	Oral polio vaccine
RCT	Randomised controlled trial
TB	Tuberculosis

# 1 INTRODUCTION

## 1.1 Vaccines and non-specific effects

WHO recommends home visits after birth to reduce neonatal mortality. Guinea-Bissau has not implemented such home visits yet. Vaccinations are normally provided at the health centre, the current vaccination policy is to provide Bacillus Calmette-Guérin vaccine (BCG) and oral polio vaccine (OPV) at birth, pentavalent vaccine (diphtheria-tetanus-pertussis-H. influenzae type B-Hepatitis B vaccine), OPV and pneumococcal vaccine at 6, 10, and 14 weeks, rota-virus vaccine at 6 and 10 weeks, inactivated polio vaccine at 14 weeks, and measles vaccine (MV) and yellow fever vaccines at 9 months (Figure 1).

BCG: Bacillus Calmette-Guérin vaccine, OPV: Oral Polio vaccine

Penta: Diphtheria, Pertussis, Tetanus, Haemophilus Influenzae B, Hepatitis B

PCV: Pneumococcal vaccine, Rota: Rotavirus vaccine, IPV: Inactivated Polio Vaccine

MV: Measles vaccine, YF: Yellow Fever vaccine

**Figure 1: Recommended vaccination schedule in Guinea-Bissau**

Public health policies in low-income countries are based on a one-disease-one-solution paradigm: for each of the important diseases, a specific vaccine is developed. It is believed that the vaccine prevents only the specific disease and does nothing else. Therefore, most routine vaccinations (including MV, BCG, OPV, Diphtheria-tetanus-pertussis vaccine (DTP)) have not been tested for their effect on overall mortality.

The Bandim Health Project (BHP) has shown in numerous observational studies and randomised controlled trials (RCTs) in low-income countries that the “one-disease-one-solution” paradigm is wrong. Apart from preventing specific diseases, the vaccines may also have much wider effects on the immune system, which leads to changes in resistance/susceptibility to unrelated infections.

## 1.2 Non-specific effects of BCG

Several observational studies in Africa and other high-mortality areas show that BCG is associated with better child survival, which cannot be explained by prevention of tuberculosis (TB).

WHO recommends BCG vaccine at birth to normal-birth-weight children (NBW) in low-income

countries to prevent TB. For low-birth-weight children (LBW;<2500g) BCG vaccination is often delayed because these children are assumed to be immunologically immature, and therefore they are typically only vaccinated when they have reached 2500g. However, in two RCTs in Guinea-Bissau, BCG-at-birth reduced neonatal mortality in LBW children by 48% (95%CI: 18-67%). TB is very rare in early childhood and these strong beneficial effects can therefore not be ascribed to prevention of TB. Rather the effect is due to a beneficial training of the immune system, preventing or ameliorating other infections, which cause neonatal and childhood death. The effect of BCG-at-birth on neonatal mortality was seen already during the first three days post-vaccination, the reduction in mortality being 58% (8-81%). This rapid effect suggests that the effect is due to changes in the innate immune system rather than the adaptive immune system.

### **1.3 Biological mechanism of the effect of BCG**

Recent immunological studies have shown that BCG induces epigenetic changes in monocytes, which reprogram the innate immune system to increased pro-inflammatory responses against unrelated pathogens. These findings strongly support that BCG may indeed have non-specific beneficial effects, protecting the recipients not only against TB, but against non-targeted infectious diseases.

## **2 JUSTIFICATION**

BCG is rarely given at birth in rural areas in low-income countries; in rural Guinea-Bissau only 38% are vaccinated with BCG in the first month of life. A major reason for this delay is the immunization programme (EPI)'s focus on reducing wastage of vaccines. Freeze dried vaccines like BCG have to be used within 6 hours after reconstitution with a diluent. Therefore, a vial of BCG vaccine, which contains 20 doses, is not opened unless 10-12 children are present to be vaccinated. Hence, there are many missed vaccination opportunities. This delay in BCG vaccination may be very important. Approximately 75% of neonatal deaths occur within the first week of life and only 11% of the children receive BCG in the first week of life. If BCG vaccine indeed has profound effects on innate immunity and neonatal mortality and morbidity in both LBW and NBW children many lives could be saved if BCG was provided earlier.

## **3 AIM**

In the present randomised trial, we aim to study the effect of BCG and OPV vaccinations provided at a single home visit within 72 hours after birth on early infant mortality and morbidity among infants in a rural and an urban area in Guinea-Bissau.

## 4 HYPOTHESIS

BCG at birth provided at a single home visit shortly after birth will reduce early infant non-accidental mortality by 40% between the home visit and the subsequent home visit or pentavalent vaccine.

## 5 METHODS

### 5.1 Setting

The study will be conducted in Bandim Health Project's Health and Demographic Surveillance System (HDSS) site in rural and urban Guinea-Bissau.

#### 5.1.1 The rural HDSS

The rural HDSS was established in 1990. The BHP teams survey women of fertile age and their children below the age of 5 years in randomly selected clusters of villages in all the nine health regions in the country. Children in the three rural regions closest to Bissau (Oio, Biombo and Cacheu) will be eligible for the study.

The rural clusters are followed with two-monthly visits by the mobile teams. At all visits the women are asked whether they are pregnant. When a pregnancy is registered; the woman's nutritional status is assessed by measurement of a mid-upper-arm-circumference (MUAC); information on antenatal care is collected prior to giving birth, as well as at the first visit after delivery. Socio-economic factors (type of roofing, type of bathroom, possession of a mobile phone, radio and generator) are registered. After the delivery, information on the place of delivery (home, health facility) and who assisted the delivery is collected.

#### 5.1.2 The urban HDSS

The urban HDSS was established in 1978. Fieldwork assistants follow children below the age of 3 years through home visits every third month. Pregnancies are registered every month and followed monthly until birth. When a pregnancy is registered information on ethnic group, gestational age, use of mosquito net is collected. After the delivery, information on place of delivery (home, health facility) is collected. Children in the urban study area will be eligible for the study.

#### 5.1.3 Study nurses

For the present study, we will select study nurses to conduct home visits. The study nurses will be selected in collaboration with the regional health authorities of Oio, Biombo, and Cacheu. They will be selected among nurses working at a health centre with a catchment area, which corresponds to the study cluster in order to allow them to carry out the project visits in addition to their normal routines. For the urban study area, the BHP will employ a study nurse fulltime. The nurses will use

a project motorbike to visit new-borns at home. They will receive a monthly salary subsidy, and a subsidy for each home visit conducted shortly after birth of the child.

#### 5.1.4 Community Key Informants

To ensure that the nurses are informed immediately about deliveries, we will use community key informants (CKI) in the rural area. A CKI will be selected among residents in each rural village to collect information about pregnancies, deliveries and deaths. Where possible, the CKI will be the community health worker (ASB). The CKI will communicate immediately any delivery in the village to the study nurse. In the urban area, we will take advantage of the close follow-up by the fieldwork assistants that circulate the zones each day. To carry out the job, the CKI or fieldwork assistant will receive a subsidy for each timely call about a new-born.

## 5.2 Study design and randomisation

We will conduct a cluster-randomised trial, randomising clusters to two different treatment groups, stratified by region and pre-trial mortality level (high/low). Pre-trial mortality level is assessed using the BHP rural HDSS data from 2012 to 2015. Pre-trial mortality level in the urban area will be based on the BHP urban HDSS data from 2013 to 2016, to account for a change in the registration system in 2012.

Randomisation of clusters will be by computer generated random numbers. All new-borns will be visited as soon as possible after birth. To children in half of the clusters we will provide standard care and vaccines (BCG, OPV) at the home visits; children in the remaining clusters will only receive standard care but no vaccines (Table 1).

## 5.3 Sample size considerations

Based on previous data from the rural HDSS in the areas where the current study will be conducted, the expected proportion of events (deaths and hospitalisation) between day 1 and the next home visit or 60 days of age, whichever comes first is 2.4% (unpublished data). We expect the proportion of events to be at least as high in the urban area. A recent trial in Ghana indicated that three home visits during the first week of life to promote essential new-born care practices and to weigh and assess children for danger signs was associated with an 8% (-12 to 25%) reduction in neonatal mortality. Based on pre-trial mortality data from the same rural clusters, we estimate the design effect to be 1.35 (ratio of square of the standard errors for the cluster-adjusted/unadjusted HRs). Thus, in order to obtain 80% power to detect a reduction in early infant severe morbidity if the true reduction of BCG and OPV provided at home visits is larger than 40%, we will need to enrol at least 6666 children.

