### 5.4.5 Exclusion criteria

There are very few exclusion criteria, because the study is expected to answer a pragmatic question about the effect of BCG and OPV vaccination at home visits shortly after birth.

- Children born outside the cluster, and returning more than 72 hours after the delivery
- Children that the nurse evaluates to die within the next 24 hours.

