### 5.7 Statistical analyses

All children registered during pregnancy will enter the study when they are visited at home or 24 hours after birth, whichever comes last, thereby excluding deaths and hospital admissions on the day of birth.

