#### 5.7.2 Analyses of outcomes

The data will be analysed on individual level data to account for varying cluster sizes. We will use the conventional 5% significance level and 95% confidence interval. Below are a summary of the planned analysis. Further details are provided in the analysis plan in the appendix.

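### The 2.4% planning proportion counts events from day 1, but the per-protocol analysis starts at the home visit and omits moribund children, so the stated 80% power is modestly overstated

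*Protocol*

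**What the plan says.** **Planning figure.** Protocol 5.3 gives 2.4% as the expected proportion of "events (deaths and hospitalisation) between day 1 and the next home visit or 60 days of age", whichever is earlier, from unpublished rural surveillance data. It expects the urban proportion to be no lower. With a design effect of 1.35, at least 6666 children are to be enrolled "in order to obtain 80% power to detect a reduction in early infant severe morbidity", for an effect above 40%. Protocol 5.5.1 explains that the sample size was set for the composite while mortality stays the primary outcome.

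**Start of follow-up.** Protocol 5.7 says that children "will enter the study when they are visited at home or 24 hours after birth, whichever comes last". SAP Appendix 2 repeats this in Table 2 (mortality) and Table 8 (composite), and the outline code enters each child at the later of the day after birth and the enrolment date. The per-protocol population is limited to children visited within 72 hours (Protocol 5.7.3; SAP Appendix 1, section 1).

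**Moribund children.** Protocol 5.4.5 excludes "Children that the nurse evaluates to die within the next 24 hours", and SAP Table 2 does the same. Table 8 uses the same population. Visited moribund children return only in the intention-to-treat analysis (Protocol 5.7.6; SAP Appendix 2, section 5). SAP Appendix 1 rests the main conclusion on the per-protocol analysis.

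**Early risk.** Protocol section 2 states: "Approximately 75% of neonatal deaths occur within the first week of life".

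**The concern.** The planning proportion and the analysis do not count the same events. Two groups of events are in the first and not in the second:

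- deaths and admissions between 24 hours and the visit, in children visited after 24 hours;
- deaths of children judged moribund at the visit.

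Both differences push the same way, and the time removed falls in the first week, when the protocol itself places most neonatal deaths. Nothing in 5.3 adjusts the 2.4% or the 6666. The composite was chosen to carry the sample size because mortality alone may be inconclusive, so its event proportion supports the whole power statement. If it is too high, a null composite result is harder to interpret: a reader cannot tell absence of effect from fewer events than planned.

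**Working it through.** **1. Inputs.** From Protocol 5.3: 2.4%, a 40% reduction (ratio 0.60), 80% power, design effect 1.35, N = 6666. Protocol 5.7.2: "We will use the conventional 5% significance level and 95% confidence interval". SAP Appendix 1: two-tailed tests. Allocation is half the clusters to each arm (Protocol 5.2).

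**2. The plan's own figure.** Section 5.3 states no formula, so several readings were tried.

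- 2.4% as the proportion over both arms. Schoenfeld events = 4 × (1.960 + 0.842)² / (ln 0.60)² = 120.3. N = 120.3 / 0.024 × 1.35 ≈ 6768, which is 1.5% above 6666. Power at 6666 is 79.4%.
- 2.4% in controls against 0.60 × 0.92 × 2.4% = 1.325%, two-sided, two proportions, × 1.35: 6699. This brings in the 8% home-visit effect cited in 5.3, whose use there is not stated.
- 2.4% against 1.44%, one-sided 5%, × 1.35: 6820. This conflicts with the two-tailed rule.
- 2.4% against 1.44%, two-sided, × 1.35: 8659. This does not reproduce 6666, and power at 6666 is about 69%.

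The figure can be approached, but the documents do not say which arm the 2.4% describes.

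**3. Where the windows differ.** Take day 1 as the day after birth, the reading kindest to the plan.

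| | Planning figure | Per-protocol analysis |
|---|---|---|
| Day-of-birth events | out | out |
| 24 hours to visit, child visited after 24 hours | in | out |
| Deaths of moribund children after 24 hours | in | out |
| After the visit, to next visit or day 60 | in | in |

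**4. How much might be lost to visit delay (assumptions).** Suppose one third to one half of first-week neonatal deaths fall on day 0 and the rest are spread evenly over days 1 to 7. Of all neonatal deaths, W = 50% to 37.5% then fall later in week 1, and 25% after week 1. The share of post-day-0 neonatal deaths missed is (visit day − 1)/6 × W/(W + 25).

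- All visits at 48 hours: 1/6 × 50/75 = 11%, or 1/6 × 37.5/62.5 = 10%.
- All visits at 72 hours: 22%, or 20%.
- Visits spread evenly over 0 to 72 hours: mean delay past 24 hours = (2²/2)/3 = 0.67 day, giving 0.67/6 × (0.60 to 0.67) ≈ 7%.

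These are shares of neonatal deaths. The 2.4% also includes admissions and runs to day 60. If neonatal deaths were half of composite events and no admissions were lost (both assumed), 7% becomes about 3.5%.

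**5. Effect on power.** With a share f of events lost equally in both arms, and the hazard ratio and design effect unchanged, power = Φ((1.960 + 0.842) × √(1 − f) − 1.960).

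| Events lost | Proportion left | Power from nominal 80% | 2.4% over both arms, N = 6666 |
|---|---|---|---|
| 0% | 2.40% | 80.0% | 79.4% |
| 3.5% | 2.32% | 78.6% | 78.0% |
| 5% | 2.28% | 78.0% | 77.3% |
| 10% | 2.16% | 75.7% | 75.1% |
| 20% | 1.92% | 70.7% | 70.1% |

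The last column is Φ(√(D/4) × |ln 0.60| − 1.960) with D = 6666 × proportion left / 1.35. If 2.4% is instead the control proportion, two-sided power is 69.1% with no loss, 66.8% at 5% and 64.4% at 10%.

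**The case against.** The strongest reply is that the windows mostly agree. Both leave out the day of birth and both end at the next visit or day 60. For a child visited within 24 hours the start dates coincide. Early visits are the aim: informants report births at once, and the nurse comes the same day where possible (Protocol 5.1.4, 5.4.1), so 72 hours is a limit and not the typical age. This stands, and it is why a few percent to about 10% is more plausible than 20%. It does not close the gap, because 5.3 gives no visit ages and makes no allowance.

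A second reply is that little hangs on the figure. The 80% concerns a secondary outcome, for which SAP Appendix 1 applies no significance threshold. The 6666 is a minimum, and Protocol 5.5.1 already warns that mortality may be inconclusive. An urban proportion above 2.4% could also offset part of the loss. All of this is fair. It limits the consequence but does not make the stated power correct for its stated input.

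Some stronger readings are tempting but not supported:

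- *The trial cannot count these events at all.* Visited moribund children are in the intention-to-treat analysis. Only events before any visit are outside both analyses.
- *A child admitted before the visit is never at risk.* Earlier admission is not an exclusion. That admission is not counted, but the child can enrol if visited in time and can have a later event.
- *A fifth or more of events are lost.* That share follows only for neonatal deaths with every visit at 72 hours. Nothing derives it for the composite to day 60.

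**Conclusion.** The point holds in limited form. On the documents' own definitions, the 2.4% includes events that the per-protocol analysis leaves out, and no allowance is made, so the 80% for the composite is overstated on this account. If day 1 meant the day of birth, the gap would be wider.

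The size is an assumption, not a finding. Losses of 3.5% to 10% of composite events cost about 1.4 to 4.3 points of two-sided power from a nominal 80%. A 20% loss, giving about 71%, is an upper bound for visit delay: it needs nearly all visits at 72 hours and losses as large for admissions as for deaths. The moribund exclusion adds an amount that the documents do not let one quantify.

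A reader might infer that the trial is too small or must enrol more. The documents do not support that: the loss is unknown, urban rates may offset it, and the unstated arm for the 2.4% moves power further (about 79% against 69%) than a 10% loss does.

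**What to change.** Recompute the event proportion from the same pre-trial surveillance births, with follow-up starting at the later of 24 hours and the expected age at visit. Age at enrolment is already a listed baseline variable (SAP Appendix 2, Table 1), so the trial's own visit ages can be used. Show a range for the moribund exclusion, for instance from no removal to removing every child who died within 24 hours of that starting age.

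In 5.3, state whether the proportion applies to the control arm or to both arms together, and restate the two-sided power that 6666 children give at the recomputed value.

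The cost is one tabulation of data the sponsor already holds and a reworded paragraph. Enrolment, the analysis and clinical procedures stay as they are. The downside is a slightly less favourable power statement.

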## **5.5 Outcomes**

### 5.5.1 Primary outcome: Non-accidental early infant mortality

The primary outcome is non-accidental mortality between the home visit and, the next follow-up visit by the BHP, when all unvaccinated children, who are home will be offered BCG or the date, where the first non-trial vaccine is registered by BHP. All children living in intervention and control clusters will be followed through the rural or urban HDSS routines, where information on vital

status of all followed children is collected. With declining mortality, we may however not be able to obtain conclusive result. We have therefore defined the sample size for the composite outcome, but retained mortality as the primary outcome.

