Appendix 1: General analysis principles

1 Participant population

All main analyses will be completed in a per-protocol (PP) population of all BCG-unvaccinated children, who received a home visit within 72 hours after birth, and who received the assigned treatment. The primary analysis and hence the main conclusion of the trial will be based on the PP analysis. Unless explicitly stated all analyses will be PP.

Since the cluster-size varies, data will be analysed on individual level data. All statistical tests will be 2-tailed and $p \leq 0.05$ considered statistically significant for analyses involving the primary outcome.

2 Unadjusted and adjusted analyses

Both unadjusted analyses and analyses adjusted for place of delivery will be reported. Conclusions will be based on the unadjusted analyses.

3 Multiple testing

P-values will not be corrected for multiple testing. Secondary outcomes are tested to observe if the pattern is similar across other health outcomes. Consequently, $p \leq 0.05$ will not be employed as a threshold for statistical significance for secondary outcomes. For the sensitivity analyses, we will not consider statistical significance, but rather robustness of the conclusions across different definitions of outcomes and co-variates.

4 Missing data

All analyses will be complete-case analyses.

5 Proportional hazards

To test the proportional hazards assumption, a required assumption of the Cox regression, we will perform formal significance tests based on Schoenfeld residuals. In addition, we will assess proportionality by allowing the hazard ratio to interact with the underlying timescale to identify a possible time trend. Finally, we will assess proportionality graphically via log-log survival curves.

Significance tests based on Schoenfeld residuals will be performed via the stata command *estat phtest, detail* leading to both a global test and a test for each covariate, the latter being relevant only when we study effect modifications. Presentation of log-log survival curves will be undertaken via *stphplot*. Finally, possible interactions between hazard ratios and the underlying time scale will be

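### Protocol 5.3 states 80% power with 6666 children; with 2.4% as the rate without home vaccination and the two-sided 5% test specified, power is about 70%

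*Protocol*

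**What the plan says.** Protocol 5.3 sizes the trial on severe morbidity, the composite of death and hospital admission. It expects 2.4% of children to have an event between day 1 and the next home visit or 60 days, from earlier rural surveillance data in the study areas, and it expects the urban proportion to be no lower. On clustering it says "we estimate the design effect to be 1.35". It cites an 8% reduction in neonatal mortality (interval -12 to 25%) from a home-visit trial in Ghana, without saying whether this was used. The conclusion is that "in order to obtain 80% power to detect a reduction in early infant severe morbidity", if the true reduction is "larger than 40%, we will need to enrol at least 6666 children".

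Section 5.3 names no significance level, no sidedness, no formula and no arm for the 2.4%. The test level is set elsewhere. Protocol 5.7.2 says "We will use the conventional 5% significance level and 95% confidence interval", and SAP Appendix 1 says "All statistical tests will be 2-tailed".

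The composite is a secondary outcome. Protocol 5.5.1 explains the choice: "We have therefore defined the sample size for the composite outcome, but retained mortality as the primary outcome". For secondary outcomes SAP Appendix 1 adds that p ≤ 0.05 "will not be employed as a threshold for statistical significance for secondary outcomes".

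**The concern.** This is the only power statement in the two documents. With the inputs printed beside it and the test specified elsewhere, 6666 falls well short of 80% power on the most natural reading of 2.4%. Readers will use the stated power to judge how much a null finding on severe morbidity tells them. If the chance of missing a true 40% reduction is about three in ten and not two in ten, the text overstates how informative such a finding would be. Because section 5.3 leaves out four of the items that define the calculation, nobody can confirm the figure from the text alone.

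**Working it through.** **Inputs.** Event proportion 2.4%, reduction 40% (ratio 0.60), design effect 1.35, power 80% and N = 6666 (protocol 5.3); 5% level (5.7.2); two-sided (SAP Appendix 1); half the clusters per arm (5.2), taken as 1:1 by child. Normal quantiles: 1.960 (two-sided 5%), 1.645 (one-sided 5%), 0.842 (80% power). (ln 0.60)² = 0.2609.

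If 2.4% applies without home vaccination, the vaccinated proportion is 0.024 × 0.60 = 1.44%, and the mean over both arms is 1.92%.

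**The plan's figure.** Schoenfeld's formula with one-sided 5%:
- Events: 4 × (1.645 + 0.842)² / 0.2609 = 94.8
- Children before clustering: 94.77 / 0.0192 = 4,936
- Times 1.35: 6,664. Rounding up to whole children per arm first (2 × 2,469 = 4,938) gives 6,666.3.

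**Same inputs, two-sided 5%.**
- Schoenfeld events: 4 × (1.960 + 0.842)² / 0.2609 = 120.3
- Children: 120.3 / 0.0192 = 6,266; times 1.35 = 8,460
- Two proportions (2.4% against 1.44%, no continuity correction): 6,413 × 1.35 = 8,657

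**Power at 6666, two-sided 5%.**
- Effective events: 6666 × 0.0192 / 1.35 = 94.8
- Schoenfeld: Φ(0.5108 × √(94.8 / 4) − 1.960) = Φ(0.527) = 70%
- Two proportions, with 6666 / (2 × 1.35) = 2,469 effective children per arm: 69%

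**What 6666 does give at 80% power, two-sided 5%.** At 2.4%, a reduction of about 44% (Schoenfeld) to 45% (two proportions). At a 40% reduction, a control proportion of about 3.0% (Schoenfeld) to 3.1% (two proportions).

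**Other routes to a figure near 6666.**

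| Reading | Formula | N |
|---|---|---|
| One-sided, 2.4% in controls | Schoenfeld | 6,664 |
| One-sided, 2.4% in controls | Two proportions | 6,819 |
| Two-sided, 2.4% as mean of both arms | Schoenfeld: 120.3 / 0.024 × 1.35 | 6,768 |
| Two-sided, 2.4% against 0.024 × 0.92 × 0.60 = 1.325% | Two proportions | 6,698 |

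In the third row, power at 6666 is 79.4%, and the control proportion would have to be 0.024 / 0.8 = 3.0%. The fourth row credits the 8% home-visit effect to the intervention arm alone. That is not a valid comparison, because 5.4.2 gives the nurse's visit and examination to all children.

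**Sensitivity.** If the 8% carried over to the composite in both arms, the control proportion would be 0.024 × 0.92 = 2.21%. Power at 6666 would then be about 66% (Schoenfeld) or 65% (two proportions).

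**The case against.** A reader might infer that 6666 can be obtained only from a one-sided calculation, and so that the authors used one. The documents do not support this. Section 5.3 states no sidedness, the close match depends on the formula (one-sided two proportions gives 6,819), and two two-sided routes come within about 2%.

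The best defence of the figure is that 2.4% is not tied to an arm. As the mean over both arms it gives 79.4% power two-sided, in practice the stated 80%. The text does not exclude that reading. It is the less natural one, because the figure comes from surveillance before the trial and because it implies about 3.0% in controls, a value that appears nowhere. Even then the requirement is 6,768, slightly above the stated minimum.

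Section 5.3 also words its inputs as bounds: an urban proportion at least as high, a reduction larger than 40%, at least 6666 children. Power above 70% is therefore possible. But no higher values are given, and a power statement is judged at the values it states.

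The consequence is limited too. The composite is secondary, SAP Appendix 1 attaches no significance threshold to it, and 5.5.1 already warns that the mortality result may be inconclusive. This softens the impact but does not rescue the figure. A power of 80% has meaning only against a test level, and the documents give no level other than 5%, two-tailed.

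Finally, a reader might conclude that power is really 66% because the 8% was ignored. That goes too far. The 8% concerns neonatal mortality after three visits, with an interval that includes no effect; this trial makes one visit after birth and counts deaths and admissions to 60 days.

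**Conclusion.** The stated power does not follow from the plan's inputs on their natural reading. Power at 6666 is about 70%, 10 percentage points below the text, and 80% would need about 1,800 to 2,000 more children (8,460 − 6,666 = 1,794; 8,657 − 6,666 = 1,991). This rests on 2.4% being the proportion without home vaccination, exactly a 40% reduction, a design effect of 1.35, equal arms, and the two-sided 5% test applied to the composite. If 2.4% was meant as the mean of both arms, the stated power is nearly right, and the defect is that the text does not say so. Under either reading section 5.3 omits alpha, sidedness, formula and arm, and needs correcting. How 6666 was derived cannot be settled from the documents.

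**What to change.** Rewrite the end of protocol 5.3 to give alpha, sidedness, the formula and the arm to which 2.4% applies. If that is the control arm, suitable text would be: with 6666 children, a control proportion of 2.4%, a design effect of 1.35 and a two-sided 5% test, power is about 70% for a 40% reduction in severe morbidity, and 80% for a reduction of about 44% (or for a 40% reduction if the control proportion is about 3.0 to 3.1%). If 2.4% was meant as the mean of both arms, say so and justify the implied 3.0% in controls.

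Optionally, add about 66% power at a control proportion of 2.2%, labelled as an assumption that the cited mortality effect of home visits carries over to the composite.

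The change costs one paragraph. Enrolment, design and analysis stay as they are. The downside is that the stated power becomes less favourable.
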